#### 5.10 Trial Success

Both the primary safety and primary effectiveness endpoints must be met for trial success. Additional labeling claims may be made based on the secondary endpoints.

# 7 Acronyms and Abbreviations

Acronym/ Abbreviation	Term
6MWD	Six-Minute Walk Test Distance
6MWT	6 Minute Walk Test
A-G	Andersen-Gill
ASD	Atrial Septal Defect
AT	As-Treated
BNP	Brain Natriuretic Peptide
CDS	MitraClip Delivery System
CEC	Clinical Events Committee
CMS	Centers for Medicare and Medicaid Services
CPX	Cardiopulmonary Exercise Testing
DMC	Data Monitoring Committee
EF	Ejection Fraction
FDA	Food and Drug Administration
FMR	Functional Mitral Regurgitation
HF	Heart Failure
ITT	Intent To Treat
JFM	Joint Frailty Model
KCCQ	Kansas City Cardiomyopathy Questionnaire
LVEDD	Left Ventricular End Diastolic Dimension
LVEDV	Left Ventricular End Diastolic Volume
LVEF	Left Ventricular Ejection Fraction
LVESD	Left Ventricular End Systolic Dimension
LVESV	Left Ventricular End Systolic Volume
MI	Myocardial Infarction
MV	Mitral Valve
NT-pro BNP	N-terminal prohormone of Brain Natriuretic Peptide
NYHA	New York Heart Association
PP	Per Protocol

Acronym/ Abbreviation	Term
QoL	Quality of Life
RVSP	Right Ventricular Systolic Pressure
SAP	Statistical Analysis Plan
SAS	Statistical Analysis Software
SLDA	Single Leaflet Device Attachment
TEE	Transesophageal Echocardiogram

#### **APPENDIX A Additional Analysis for CMS**

#### A.1 Additional Clinical Outcomes for CMS

The following clinical outcomes requested by CMS will be reported for the Device and Control groups through 12 months follow-up post randomization, and compared between the Device and Control groups.

- Adjudicated stroke events at 12 months
- Adjudicated Transient ischemic attacks (TIAs) events at 12 months
- Major vascular complications (events) reported by sites at 12 months
   Major vascular complications will be reported through 12 months follow-up. Major vascular complications are defined based on the modified Valve Academic Research Consortium (VARC-2) definition as a composite of the following components:
  - a) Any aortic dissection, aortic rupture, cardiac rupture, cardiac valve rupture, ventricular rupture, arterial rupture, coronary artery perforation or cardiac perforation, or aneurysm/cardiac aneurysm/ cardiac or vascular pseudo-aneurysm
  - b) Access site or access-related vascular injury (dissection, stenosis, perforation, rupture, arterio-venous fistula, vascular pseudoaneurysm, hematoma, nerve injury, compartment syndrome) resulting in serious adverse events
  - c) Embolism (or embolus)/Thrombosis resulting in serious adverse events
  - d) Any serious adverse event resulted in medical or surgical intervention to prevent permanent impairment to body structure or body function
  - e) Any new lower extremity ischemia resulting in serious adverse events
- Renal complications reported by sites at 12 months
   Renal complications is a composite event of any acute kidney injury, renal failure, or renal insufficiency.
- Subsequent mitral valve operations (reoperations) at 12 months
   Subsequent mitral valve operations are defined to include any post "Treatment Visit" operations (open surgical or transcatheter) on the mitral valve in the Device group compared to the Control group.

-

<sup>1 Kappetein AP et al. Updated Standardized Endpoint Definitions for Transcatheter Aortic Valve Implantation – The Valve Academic Research Consortium 2 Consensus Document. Journal of the American College of Cardiology, Vol 60, No. 15, 2012.

The number and proportion of subjects with the events through 12-month follow-up will be summarized by the binary method for both Device and Control groups. Subjects lost to follow-up or withdrawal before a time point (e.g. the 12-month visit) will be excluded from the summary unless they are known to have experienced the event prior to that time point (e.g. within 12 months).

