8.1.2 Serious Adverse Event

If the AE meets any of the criteria below, it is regarded as serious adverse event (SAE).

- a) Led to a death,
- b) Led to a serious deterioration in health that either:
 - 1) Resulted in a life-threatening illness or injury, or
 - 2) Resulted in a permanent impairment of a body structure or a body function, or
 - 3) Required in-patient hospitalization or prolongation of existing hospitalization, or
 - 4) Resulted in medical or surgical intervention to prevent life threatening illness or injury or permanent impairment to a body structure or a body function.
- c) Led to fetal distress, fetal death or a congenital abnormality or birth defect.
- d) An important medical event that may not result in death, be life-threatening, or require hospitalization but may be considered serious when, based upon appropriate medical judgment, may jeopardize the subject and/or may require intervention to prevent one of the outcomes listed in this definition

Note 1: This includes device deficiencies that might have led to a serious adverse event if a) suitable action had not been taken or b) intervention had not been made or c) if circumstances had been less fortunate. These are handled under the SAE reporting system.

Note 2: A planned hospitalization for pre-existing condition, or a procedure required by the Clinical Investigation Plan, without a serious deterioration in health, is not considered to be a serious adverse event.

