#### A.2 CMS Subgroup Analysis

The following clinical outcomes will be analyzed by age subgroups (Age < 65 vs. Age  $\ge 65$ ) using Kaplan-Meier estimates. The treatment comparison in the age subgroup analysis is not powered for hypothesis testing and is not meant for confirmatory inference. Comparisons will be made between treatment arms within each age subgroup.

- Stroke at 12 months
- Major vascular complications (events) at 12 months
- Renal complications at 12 months
- All-cause mortality at 12 months

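### As worded, component (d) of the CMS major vascular complications composite is not limited to vascular events, so the between-arm comparison could include non-vascular events and could point the wrong way.

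*SAP*

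**What the plan says.** SAP Appendix A.1 lists outcomes requested by CMS, among them "Major vascular complications (events) reported by sites at 12 months". The definition is described as based on a modified VARC-2 definition and has components (a) to (e):

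- (a) lists named ruptures, dissections, perforations and aneurysms of the heart or vessels.
- (b) begins "Access site or access-related vascular injury".
- (c) is embolism or thrombosis leading to serious adverse events.
- (d) is "Any serious adverse event resulted in medical or surgical intervention to prevent permanent impairment to body structure or body function".
- (e) is "Any new lower extremity ischemia resulting in serious adverse events".

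The outcomes are to be reported by arm through 12 months "and compared between the Device and Control groups", and the subject-level proportions are "summarized by the binary method for both Device and Control groups". Appendix A.2 repeats the outcome, as "Major vascular complications (events) at 12 months", by age below 65 versus 65 and over, using Kaplan-Meier estimates. SAP Section 5.7.6 says these data go to CMS in a separate report, when results are submitted to FDA.

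**The concern.** Component (d) carries no vascular, access-site or procedural limit. Its wording is close to criterion b)4 of the general definition of a serious adverse event in Protocol Section 8.1.2: "Resulted in medical or surgical intervention to prevent life threatening illness or injury", which then continues to permanent impairment. That criterion applies to every organ system. A site or programmer who follows the SAP text would therefore count, for example, a renal or infectious event as a major vascular complication if it met (d).

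The error would not be neutral between arms. Device subjects undergo femoral venous and transseptal access (Protocol Section 6.8.6). Control subjects have a physical examination and medication review at the corresponding visit (Protocol Section 6.10). Access-related harm therefore belongs almost entirely to Device, while the SAP assumes more hospitalizations in Control. Non-vascular events entering through (d) would tend to raise the Control proportion more and offset a real vascular excess with the device. The outcome is site-reported, whereas stroke and TIA in the same list are adjudicated, and A.1 does not ask for results by component. The contribution of (d) could then not be read from the total.

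**Working it through.** The plan states no expected rate or power for this composite, so there is no figure to reproduce. The rates used below agree with the reductions the SAP attaches to them: 1 − 0.42/0.60 = 30% (stated 30%) and 1 − 1.4/1.9 = 26.3% (stated 26%).

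**Inputs from the documents**
- HF hospitalization rate per 12 months: 0.60 Control, 0.42 Device (SAP 5.8.2).
- All-cause hospitalization rate per 12 months: 1.9 Control, 1.4 Device (SAP 5.8.4.8).
- Gamma frailty with mean 1 and variance 1 (SAP 5.8.2).
- Protocol Appendix F places vascular trauma and vessel perforation in its common band, at least 1% and below 10%.

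**Assumptions**
- q, the share of hospitalizations classified under (d), is not in the documents and is left free.
- v, the Device rate of true vascular complications, is 1%, 2%, 5% or just under 10% (9.99% in the arithmetic). The Control rate is 0.
- True vascular events are independent of the events entering through (d). Death and attrition are ignored.

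**Formulas**

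With gamma frailty of variance 1, P(at least one event in 12 months) = 1 − 1/(1 + rate). On the HF rates:
- Control composite = 1 − 1/(1 + 0.60q)
- Device composite = 1 − (1 − v)/(1 + 0.42q)

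The two are equal when 1 + 0.42q = (1 − v)(1 + 0.60q), that is, q = v/(0.18 − 0.60v). The same steps with 1.9 and 1.4 give q = v/(0.50 − 1.9v). Above these values the composite favours Device although all true vascular events are in Device.

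| v | HF rates | All-cause rates |
|---|---|---|
| 1% | 0.01/0.174 = 5.7% | 0.01/0.481 = 2.1% |
| 2% | 0.02/0.168 = 12% | 0.02/0.462 = 4.3% |
| 5% | 0.05/0.150 = 33% | 0.05/0.405 = 12% |
| just under 10% | 0.0999/0.12006 = 83% | 0.0999/0.31019 = 32% |

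**Two cases on the HF rates**
- q = 50%, v = 2%: Control 1 − 1/1.30 = 23.1%; Device 1 − 0.98/1.21 = 19.0%. The true vascular rates are 0% and 2%. Of Device subjects with the composite, 0.98 × (1 − 1/1.21)/0.190 = 89% have no vascular event.
- q = 5%, v = 5%: Control 1 − 1/1.03 = 2.9%; Device 1 − 0.95/1.021 = 7.0%. The direction is correct, and 0.95 × (1 − 1/1.021)/0.0695 = 28% of Device cases are non-vascular only.

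**When most Device cases are non-vascular only**

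This requires (1 − v)(1 − 1/(1 + 0.42q)) > v, that is, q > v/[0.42(1 − 2v)]. The thresholds are 2.4%, 5.0%, 13% and 30% for the four values of v.

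**The case against.** The best defence is context. Component (d) sits under a vascular heading and cites a vascular definition. Stroke, TIA, renal complications and mitral reoperations are listed as separate outcomes, and a literal (d) would absorb many of them. A vascular limit was probably intended. That stands as evidence of intent, but no operative text states the limit. The definition is called modified, so limits in the cited source cannot be assumed to carry over.

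Several narrower objections also stand:

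- Component (d) does not catch every serious adverse event that needed intervention. The intervention must be to prevent permanent impairment, and (d) omits the life-threatening limb of criterion b)4.
- Protocol Section 8.1.2 lists hospitalization (b)3) apart from intervention (b)4), so hospitalization rates are only a rough proxy for (d). The HF hospitalization definition in Protocol Appendix A does require intravenous or invasive treatment, or death in the emergency department. Some such admissions could therefore plausibly be classified under (d), but how many is unknown.
- A reader might infer that the wording would conceal access-site harm altogether. The documents do not support that. Device- or procedure-related adverse events adjudicated by the Clinical Events Committee are reported separately, split at 30 days (Protocol 7.6.1, SAP 5.7.1), as is major bleeding at 30 days (SAP 5.7.4).
- The CMS outcomes are outside the testing sequence in SAP 5.9, and A.2 says its age comparisons are not confirmatory.

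**Conclusion.** The concern holds as a defect in the definition: the text of (d) does not measure what the composite's label says. The comparison sent to CMS could include non-vascular events and could favour Device when all true vascular events are in Device. Whether it would do so depends on q, which the documents do not give, and on v, for which they give only a broad band. The thresholds run from 2.1% (all-cause rates, v = 1%) to 83% (HF rates, v just under 10%). They are approximate, because death and attrition are ignored and the Control vascular rate is set to 0.

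Two stronger readings are tempting. One is that the reported rate would be mostly non-vascular; the case q = 5%, v = 5% contradicts this. The other is that the composite would be insensitive to the true vascular rate; the table shows that the direction depends on v throughout. Neither is established.

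The effect is confined to the descriptive CMS outcomes. No primary or secondary endpoint, error rate, power or sample size changes.

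**What to change.** In SAP Appendix A.1, insert the words vascular or access-site before serious adverse event in component (d), and leave its intervention and permanent-impairment conditions as they are. Add a sentence requiring each of components (a) to (e) to be reported by arm alongside the composite. The corrected definition then carries over to Appendix A.2.

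Do not delete (d). The outcome was requested by CMS, the cited definition cannot be checked from these documents, and deletion could lose a vascular event that no other component covers.

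The cost is one phrase and one reporting line in the SAP, with no new data collection.

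### SAP Appendix A estimates stroke, major vascular and renal complications by a crude proportion for all ages and by Kaplan-Meier within age groups, so the rates sent to the payer need not reconcile

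*SAP*

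**What the plan says.** Appendix A.1 (Additional Clinical Outcomes for CMS) lists adjudicated stroke, TIA, major vascular complications, renal complications and subsequent mitral valve operations. They are to be reported "through 12 months follow-up post randomization, and compared between the Device and Control groups". The closing paragraph of A.1 sets the estimator: counts and proportions, "summarized by the binary method for both Device and Control groups". For dropouts the rule begins: "Subjects lost to follow-up or withdrawal before a time point (e.g. the 12-month visit) will be excluded from the summary unless they are known". The exception is for dropouts whose event is on record by then. Nothing is said about subjects who die without the event.

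Appendix A.2 (CMS Subgroup Analysis) splits subjects at age 65 and analyses stroke, major vascular complications, renal complications and all-cause mortality "using Kaplan-Meier estimates. The treatment comparison in the age subgroup analysis is not powered for hypothesis testing". It adds that "Comparisons will be made between treatment arms within each age subgroup". A.2 does not state how deaths are handled for the three non-fatal outcomes. SAP 5.7.4 states, for the Kaplan-Meier analysis of the primary safety components, that both deaths and withdrawals are censored.

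Stroke, major vascular complications and renal complications therefore appear in both parts under different estimators. All-cause mortality appears only in A.2. No text reconciles the two methods.

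**The concern.** A reader of the payer report would expect an all-age rate to lie between the rates of the two age groups that make it up. That holds when one proportion is used throughout, because the all-age figure is then a weighted average of the two. It need not hold here, because A.1 and A.2 treat two kinds of subject differently:

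- **Dropouts without an event.** A.1 deletes them altogether, although a dropout who had an event stays in numerator and denominator. Kaplan-Meier keeps them at risk until they leave.
- **Deaths without an event.** As A.1 is worded, they stay in the denominator as non-events. Kaplan-Meier censors them, so it estimates the risk in a hypothetical setting where nobody dies first.

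The two features work in opposite directions. At stake is whether the figures sent to the payer, described in SAP 5.7.6, agree with each other and estimate the actual 12-month incidence in this high-mortality population.

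**Working it through.** **No figure to reproduce.** The SAP gives no rate, sample size or power for these outcomes, so the check compares the estimators under the SAP's own mortality and attrition.

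**Inputs.** SAP 5.8.3.2: 12-month mortality 27% (Control) and 22% (Device), attrition 7.5% in both groups. SAP 5.8: 305 subjects in the Device group of 610. The documents give no 12-month rates for the three outcomes; the nearest figure is stroke 2% at 30 days (SAP 5.8.3.1, Table 2). Event hazards of 0.02, 0.12 and 0.30 per year are therefore assumptions, as are constant hazards and independence of death and withdrawal.

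**Formulas, over one year.** Event hazard h1; death hazard h2 = -ln(1 - mortality); withdrawal hazard h3 = -ln(1 - attrition); T = h1 + h2 + h3.

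- True incidence = h1/(h1+h2) × (1 - exp(-(h1+h2)))
- A.1 = E/(1 - W), where E = (h1/T)(1 - exp(-T)) is the observed event fraction and W = (h3/T)(1 - exp(-T)) is the event-free withdrawal fraction
- Kaplan-Meier = 1 - exp(-h1)

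**Control, h1 = 0.12.** h2 = -ln(0.73) = 0.3147 and h3 = -ln(0.925) = 0.0780, so T = 0.5127.

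- True incidence = 0.12/0.4347 × (1 - exp(-0.4347)) = 9.7%
- E = 0.0939, W = 0.0610, so A.1 = 0.0939/0.9390 = 10.0%
- Kaplan-Meier = 1 - exp(-0.12) = 11.3%

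| Mortality | h1 | True incidence | A.1 | Kaplan-Meier |
|---|---|---|---|---|
| 27% | 0.02 | 1.70% | 1.75% | 1.98% |
| 27% | 0.12 | 9.7% | 10.0% | 11.3% |
| 27% | 0.30 | 22.4% | 22.9% | 25.9% |
| 22% | 0.12 | 10.0% | 10.3% | 11.3% |

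At 7.5% attrition and 27% mortality, the dropout rule raises A.1 above true incidence by 2.3% to 3.0% relative. At 15% attrition with h1 of 0.12 or 0.30, the excess is 4.9% to 5.8%. Kaplan-Meier exceeds true incidence by about 16% relative at 27% mortality and about 13% at 22% (h1 = 0.12).

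**Direction, by hand.** Take age groups of 100 and 200 with 10% events, 22% deaths and about 7.5% withdrawals (7 and 15), with deaths and withdrawals at month 6 and all event-free at that time. A.1 for all ages = 30/(300 - 22) = 30/278 = 10.8%.

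- Events at month 9: Kaplan-Meier = 10/(100 - 22 - 7) = 10/71 = 14.1% and 20/(200 - 44 - 15) = 20/141 = 14.2%. Both lie above.
- Events at month 1: Kaplan-Meier = 10/100 and 20/200, both 10.0%. Both lie below.
- No deaths, events at month 9: Kaplan-Meier = 10/93 = 10.8% and 20/185 = 10.8%. Each equals the A.1 proportion for its own group, and the all-age figure lies between them.

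The last case is general. Without deaths, A.1 was never below Kaplan-Meier on the same data (no exception in 9,832 enumerated small data sets). Since the all-age A.1 rate is a weighted average of the group A.1 rates, both Kaplan-Meier rates cannot exceed it.

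**Frequency in simulated Device arms of 305** (2,000 runs per setting, equal risk in both age groups, assumed under-65 share 25% or 50%, event risk 5% to 20%):

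| Setting | Both age groups above | Both below |
|---|---|---|
| Events spread over the year, deaths kept in A.1 | 25-51% | 0% |
| Events in the first 30 days, deaths kept in A.1 | 0% | 15-34% |
| Deaths also excluded from A.1, either timing | 0% | 49-98% |

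**The case against.** The strongest reply is that these are descriptive outputs. They lie outside the testing sequence (SAP 5.9) and trial success (SAP 5.10). A.2 names its method and disclaims confirmatory use. Two different estimands are not an arithmetical contradiction. The bias from the A.1 rule is small: 0.3 points at about 10% incidence, against a standard error of about 1.7 points for one arm (√(0.10 × 0.90/305)). SAP 5.7 already supplies Clopper-Pearson and Newcombe intervals for proportions. The outcomes were requested by the payer, and any reporting format in that request is not visible here. All of this stands, and it limits the weight of the point. It does not supply a reason for two estimators or a rule for deaths.

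Three stronger readings are tempting and are not supported:

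- A reader might infer that the dropout rule by itself can put both age-group rates above the all-age rate. It works the other way, because it raises A.1. The excess needs event-free deaths that are counted in A.1 and censored in A.2.
- A reader might infer that both age groups will usually exceed the all-age rate. Under constant hazards, 27% mortality and an assumed 18% under 65, that occurs in 50% of simulated arms at h1 = 0.12 and 66% at h1 = 0.30. With 70% of events assumed in the first 30 days (22% mortality), both are above in only 3-4% and both below in 6-7%. Major vascular complications include access-site injury, so early clustering in the Device group is plausible.
- A reader might infer that the lack of a treatment-by-age interaction is a further error. The subgroup interaction tests in SAP 5.6.1.10 concern the primary effectiveness endpoint, and A.2 is declared non-confirmatory. A noisy mortality estimate in a small under-65 group is ordinary subgroup imprecision, which a change of estimator would not cure.

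**Conclusion.** The point holds as a minor inconsistency in SAP Appendix A. Three outcomes have two estimators, neither of which is the actual 12-month incidence. The all-age proportion is biased slightly upward by its dropout rule. The age-group Kaplan-Meier figures are biased upward by more, by about 13-16% relative under the SAP's 22-27% mortality with constant hazards. The gap between the two estimators also differs by arm, at about 1.3 points in Control (11.3% less 10.0%) and 1.0 in Device (11.3% less 10.3%) at h1 = 0.12. The rates therefore need not reconcile, and the direction of the mismatch depends on when events occur.

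The sizes rest on assumed event rates, event timing and independent death and withdrawal. They also rest on reading A.1 as keeping event-free deaths in the denominator and A.2 as censoring them. The first follows from the wording, the second from the method and from the practice in SAP 5.7.4. All-cause mortality is unaffected, since it is not in A.1. No primary or secondary conclusion changes.

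**What to change.** For stroke, major vascular complications and renal complications, use one estimator in both A.1 and A.2: 12-month cumulative incidence from randomization (Aalen-Johansen), with death as a competing event and dropouts censored at last contact. Report the arm difference with a 95% confidence interval. Remove the exclusion rule for these rates, and state the handling of deaths explicitly. Raw event counts can still be listed beside the rates. A descriptive treatment-by-age estimate may be added but is optional.

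The cost is appendix wording and standard code on data already collected. The drawback is that the A.1 rates are no longer plain counts over subjects. If the payer requires a crude proportion, it can be shown as well, labelled as such and with its treatment of deaths and dropouts stated.

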#### A.2 CMS Subgroup Analysis

The following clinical outcomes will be analyzed by age subgroups (Age < 65 vs. Age  $\ge 65$ ) using Kaplan-Meier estimates. The treatment comparison in the age subgroup analysis is not powered for hypothesis testing and is not meant for confirmatory inference. Comparisons will be made between treatment arms within each age subgroup.

- Stroke at 12 months
- Major vascular complications (events) at 12 months
- Renal complications at 12 months
- All-cause mortality at 12 months
